11.3. Eliciting Adverse Event Information

At every study visit, subjects must be asked a standard, non-directed question, such as, “How have you been feeling since your last visit?” to elicit any medically related changes in their well-being. They may also be asked if they have been hospitalized, had any accidents, used any new medications, or changed concomitant medication regimens (including prescription drugs, over-the-counter medications, vitamins, herbal products, and minerals). Responses must be documented in the source documents.

In addition to subject observations, AEs must be documented for any clinically significant diagnosis resulting from abnormal laboratory test values, physical examination findings, or ECG abnormalities, or from other documents that are relevant to subject safety.

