This prospective open label trial will study the safety, tolerability, and efficacy of hydroxychloroquine 400 mg po in qualified health care workers.

Qualified individuals will be prescribed oral hydroxychloroquine 400 mg twice a day (two 200 mg tablets twice a day) on day 1 followed by two 200 mg tablets once a week for a total of 7 weeks. Dose de-escalation is permitted during the study if indicated clinically. Please refer to [Section 7.3.1](#) for additional details on dose escalation and dose de-escalation.

All study individuals will follow the same visit and assessment schedule. Following study recruitment, participants will be scheduled to be assessed in person during treatment at days 7, 14, 21, 28, 35, 42 and 49.

Healthcare workers who are qualified for the trial but decline participation in receiving the treatment will form the control group and will be offered an observational registry where the same NP COVID-19 sampling schedule and other assessments will be followed with the exception of blood testing. The clinical outcomes will be captured in the same manner and with the same definitions as the clinical arm.

Number of Subjects (planned):

360 individuals will be enrolled into the study with half enrolling in the active treatment study and the other half, those who refuse to get the study treatment, will be entering an observational registry considered as the control group.

Main criteria for inclusion:

1. Adult male and female healthcare workers ≥ 18 to ≤ 75 years of age upon study consent
2. Healthcare workers with
 - One day or more of exposure to suspected and/or positive COVID-19 patients, including but not limited to those working in the Emergency Department or Intensive Care Unit.OR
 - Unprotected exposure to a known positive COVID-19 patient within 72 hours of screening.
3. Afebrile with no constitutional symptoms
4. Willing and able to comply with scheduled visits, treatment plan, and other study procedures
5. Evidence of a personally signed and dated informed consent document indicating that the subject (or a legally acceptable representative) has been informed of all pertinent aspects of the study prior to initiation of any subject-mandated procedures

Major exclusion criteria:

1. Participation in other investigational clinical trials for the treatment or prevention of SARS-COV-2 infection within 30days

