5.1.3. Transaminase and GGT Elevations

In clinical studies of hydroxychloroquine, patients may have increases of transaminase enzymes above baseline upon initiation of treatment, please refer to the package insert for a detailed discussion.

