5.1.5. Anemia

Clinical studies of hydroxychloroquine, patients may have reductions in hemoglobin from baseline upon initiation of treatment, please refer to the package insert for a detailed discussion.

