5.1.6. Prolonged QT and Risk for Arrhythmias

Hydroxychloroquine may prolong the QT interval. Please refer to the package insert for a detailed discussions.

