9.4.1. Study Monitoring Committee

A study monitoring team including a qualified physician, a monitor from BSWRI, and a statistician will be responsible to monitor the safety and integrity of the study and to make recommendations as appropriate. They will start reviewing the collected data approximately 4

weeks after the first subject is enrolled and will continue to do so quarterly until the last dose of the last subject enrolled.

The study monitoring committee will be responsible for reviewing the progress of the study and the accumulating of the data while the study is ongoing. They may recommend that the study continue as is, be modified to protect subject safety, or be terminated. However, investigators, will make decisions concerning the need for laboratory investigations, ECG, and intra-subject dose-escalation decisions throughout the study for each subject and may choose to decrease the subject's dose (to one-half of the prior dose).

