9.5. Unscheduled Visits

Unscheduled visits are allowed for the following reasons:

- Management of an adverse event or serious adverse event;
- Dose de-escalation;
- Any time the investigator feels that it is clinically appropriate for subject safety.

At a minimum, unscheduled visits should include collection of adverse events and vital signs. Additional conversations may be necessary with the medical monitor following an unscheduled visit to assess subject safety.

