12.1.2. Safety Variables

The safety variables include results of vital sign measurements, adverse events, and serious adverse events.

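### No safety laboratory test or ECG is scheduled, yet diagnoses from discretionary tests count as adverse events; silent hepatic, hematologic and QT effects are not ascertained systematically, and testing may differ by group

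*Protocol*

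**What the plan says.** **Named effects.** Protocol 5.1.3 says "patients may have increases of transaminase enzymes above baseline upon initiation of treatment"; 5.1.5 says "patients may have reductions in hemoglobin from baseline upon initiation of treatment"; 5.1.6 says "Hydroxychloroquine may prolong the QT interval". Section 5.1.4 adds muscle discomfort.

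**Scheduled measures.** Table 3 lists body temperature, a cough scale, adverse event (AE) collection, an exposure questionnaire and NP swabs. It has no chemistry, hematology or ECG row. The only blood draw is optional antibody serology.

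**Discretionary tests.** Under Protocol 9.4.1 the investigators "will make decisions concerning the need for laboratory investigations, ECG" case by case. Section 11.3 then requires that "AEs must be documented for any clinically significant diagnosis resulting from abnormal laboratory test values, physical examination findings, or ECG abnormalities". Section 11.6 limits this to clinically significant laboratory changes, and requires drug-related abnormal results to be followed until they return to baseline or normal.

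**Control group.** Those who decline the drug form the control group. The Synopsis says that for them "other assessments will be followed with the exception of blood testing". Sections 11.2.1.1 and 11.6 open AE recording at the first dose.

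**Vital signs.** Protocol 12.1.2 says "The safety variables include results of vital sign measurements, adverse events, and serious adverse events", and 11.1 also lists vital signs. The safety endpoint (Protocol 6.2.4, SAP 4.4) and Table 3 have body temperature only. Section 9.5 says "unscheduled visits should include collection of adverse events and vital signs".

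**Analysis.** The SAP has no safety analysis section. SAP section 6 gives a general rule: binary outcomes are compared between groups by Chi-square or Fisher exact test.

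**The concern.** The study says it will assess safety and tolerability as well as efficacy. For three of the four effects in section 5.1, the finding is a laboratory value or an ECG interval, and the plan produces neither on a schedule. Two errors of interpretation could follow.

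- **Few events read as reassurance.** A low count of hepatic, hematologic or QT events would say little if few people were tested, and no number tested is planned as a denominator.
- **An excess read as toxicity.** The drug is known to participant and investigator, and dose decisions arise only on treatment. If treated subjects are tested more often, the same underlying rate yields more recorded AEs in that group.

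The AE window adds to this. It opens at a first dose that controls never take, so a between-group comparison has no defined start in the control group.

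**Working it through.** **1. Named effects against scheduled measures**

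| Effect in section 5.1 | What shows it | In Table 3? |
|---|---|---|
| Transaminase/GGT rise | Blood chemistry, against baseline | No |
| Muscle discomfort | Symptom report | Yes, AE collection |
| Anemia | Hemoglobin, against baseline | No |
| QT prolongation | ECG | No |

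Three of the four have no scheduled measure and no baseline value.

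**2. Inputs for the illustration**

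The documents give no rate for any of these effects, no expected number of tests and no safety power, so there is no figure of the plan to reproduce. From the sample size section: 180 per arm with 15% loss, so 180 × 0.85 = 153 evaluable per arm. Everything else below is an assumption. Let r be the true rate of abnormalities clinically significant enough to be recorded as AEs, and f the fraction of a group tested.

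**3. Loss of systematic detection**

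P(at least one case seen) = 1 − (1 − r·f)^153. With r = 2%:

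- f = 100%: 1 − 0.98^153 = 95.5%
- f = 10%: 1 − 0.998^153 = 26.4%

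With no cases seen, the one-sided 95% upper bound on the rate is 1 − 0.05^(1/number tested): 1.9% if all 153 are tested, 17.8% if 10% (15.3) are.

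**4. Unequal testing with no drug effect**

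The true rate r is the same in both groups, so the recorded rate is r·f in each. P(false significant) sums the binomial probabilities of all outcomes with two-sided Fisher p < 0.05, n = 153 per group.

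| r | Tested: treated | Tested: control | P(false significant) |
|---|---|---|---|
| 10% | 10% | 10% | 0.2% |
| 10% | 10% | 0% | 0.5% |
| 5% | 30% | 5% | 2% |
| 10% | 30% | 5% | 18% |
| 5% | 50% | 0% | 19% |
| 10% | 25% | 0% | 19% |
| 10% | 50% | 0% | 78% |

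At 30% against 5% tested and r = 10%, the recorded rates are 3.0% and 0.5%, a false ratio of 6. At r = 20% the same testing fractions give 57%, and 50% against 5% tested gives 94%.

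As single outcomes: 10% of the half tested is 153 × 0.5 × 0.10 ≈ 8 events. Then 8 against 0 gives p = 0.007, but 8 against 2 gives p = 0.10. At r = 5%, about 4 against 0 gives p = 0.12. Whether bias becomes a significant result depends heavily on assumed inputs.

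**5. Vital signs**

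Protocol 11.1 and 12.1.2 name vital signs as safety variables, while the endpoint and Table 3 have temperature only. Other vital signs can arise only at unscheduled visits, which are made for AEs, dose de-escalation or investigator judgment, and they have no baseline. SAP 4.4 already speaks of body temperature alone.

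**The case against.** **The omission is deliberate.** The study schema in the Synopsis says that standard prescribing for short-term use needs no routine health assessment. The eligibility criteria exclude chronic liver disease, blood disorders, G-6-PD deficiency and QT risk. This stands: it is a disclosed choice, not an oversight. It explains why there is no testing, but it does not supply data on these effects.

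**A reader might infer that the study cannot detect these effects at all.** The documents do not support that. Subjects are asked an open question at every visit, observed for illness and asked about hospitalization (9.8.16, 11.3). Section 11.2.1.2 requires notification of serious events after enrolment whether or not drug is taken. Symptomatic and serious cases can surface; systematic detection of silent change is what is lost. Nor does every abnormality become an AE, since 11.3 and 11.6 require clinical significance. The count of three in four applies to section 5.1 only: 9.1.3 and 9.1.4 also deal with diarrhea and nausea, which are symptoms.

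**A reader might infer that discretionary tests will fall mainly on treated subjects.** That is plausible but not stated. The blood-testing exemption may refer only to the optional serology and does not mention ECG. The Synopsis also says clinical outcomes are captured in the same way in both groups.

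**No safety comparison is specified.** This is true of the SAP as a dedicated analysis. The general rule for binary outcomes would still cover AE incidence unless it is restricted.

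**Conclusion.** The point holds in a limited form. Silent transaminase, hemoglobin and QT changes will be ascertained only through discretionary testing, without a baseline, and that testing may differ by group in an open-label, self-selected design. Clinically significant diagnoses from such tests still enter the AE counts. The direction of any bias is a reasonable inference; its size is unknown. With 153 evaluable per group and assumed true rates of 5% to 10%, the chance of a false significant difference runs from under 1% when little testing is done to 78% in the extreme case of half the treated group and no controls tested. The upper figure is not a forecast.

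Two defects need no assumption: the AE window starts at a dose that controls do not take, and vital signs are named as safety variables where only temperature is scheduled. The point concerns how safety findings are analyzed and described. Whether any test should be performed is a clinical decision not addressed here.

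**What to change.** No added procedures are needed.

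1. **SAP section 6:** keep reporting all AEs, but flag those detected only by an investigator-ordered laboratory test or ECG. Tabulate them separately and descriptively, with the number of subjects tested in each group.
2. **SAP section 6:** base the between-group AE comparison on events elicited at the scheduled visits, counted from a common start (Day 1 or enrolment) in both groups. Show the all-AE table alongside. Align Protocol 11.2.1.1 and 11.6 so that AE recording has a defined start for controls.
3. **Protocol and SAP:** state that the study draws no conclusion on asymptomatic hepatic, hematologic or QT effects.
4. **Protocol 11.1 and 12.1.2:** reconcile the vital-sign wording with Table 3 and the safety endpoint. SAP 4.4 needs no such change.

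The cost is one extra data field (event detected only by an ordered test, yes or no), a count of subjects tested, and a narrower safety claim.

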11.4. Assessment of Causality

The investigator must use the following classifications and criteria to characterize the relationship or association of the study drug in causing or contributing to the AE:

Not Related: This relationship suggests that there is no association between the study drug and the reported event.

Unlikely Related: This relationship suggests that the temporal sequence of the event with study drug administration makes a causal relationship improbable and/or other factors also provide plausible explanations.

Possibly Related: This relationship suggests that treatment with the study drug caused or contributed to the AE. That is, the event follows a reasonable temporal sequence from the time of study drug administration, and/or, follows a known response pattern to the study drug, but could have been produced by other factors.

Probably Related: This relationship suggests that a reasonable temporal sequence of the event with study drug administration exists and, based upon the known pharmacological action of the drug, known or previously reported adverse reactions to the drug or class of drugs, or judgment based on the investigator's clinical experience, the association of the event with study drug administration seems likely.

Definitely Related: This relationship suggests that a definite causal relationship exists between the drug administration and the AE, and other conditions (*e.g.*, concurrent illness, progression/expression of disease state, or concurrent medication reaction) do not appear to explain the event.

11.5. Assessment of Severity

The investigator will grade the severity of the AEs as mild, moderate, or severe using the following definitions:

Mild: Symptoms causing no or minimal interference with usual social and functional activities

Moderate: Symptoms causing greater than minimal interference with usual social and functional activities

Severe: Symptoms causing inability to perform usual social and functional activities

11.6. Recording Adverse Events

All conditions present prior to the administration of the first dose of study drug (Day 1) should be documented as medical history. After the first dose, documentation of adverse events (AEs) shall continue until 49 days following administration of the final dose of study medication, regardless of the relationship of the AE to study drug. Information to be collected includes type of event, date of onset, date of resolution, investigator-specified assessment of severity and relationship to study drug, seriousness, as well as any action taken.

While an AE is ongoing, changes in the severity (*e.g.*, worsening and improving) should be noted in the source documents, but when documenting the AE, only the total duration and greatest severity should be recorded in the eCRF. AEs characterized as intermittent require documentation of onset and duration.

All drug-related (possibly, probably, or definitely related, see [Section 11.4](#)) AEs and abnormal laboratory test results reported or observed during the study must be followed to resolution (either return to baseline or within normal limits). All other AEs will be followed through the final visit indicated in [Table 3](#), as appropriate.

AEs resulting from concurrent illnesses, reactions to concurrent illnesses, reactions to concurrent medications, or progression of disease states must also be reported. Preexisting conditions (present before the start of the AE collection period) are considered concurrent medical conditions and should NOT be recorded as AEs. However, if the subject experiences a

worsening or complication of such a concurrent condition, the worsening or complication should be recorded as an AE. Investigators should ensure that the AE term recorded captures the change in the condition (*e.g.*, “worsening of...”). Any improvement in condition should be documented per [Section Error! Reference source not found.](#)

Each AE should be recorded to represent a single diagnosis. Accompanying signs (including abnormal laboratory test values or ECG findings) or symptoms should NOT be recorded as additional AEs. If a diagnosis is unknown, sign(s) or symptom(s) should be recorded as an AE(s). Changes in laboratory test values are only considered AEs if they are judged to be clinically significant (*i.e.*, if some action or intervention is required or if the investigator judges the change to be beyond the range of normal physiological fluctuation). If abnormal laboratory test values are the result of pathology for which there is an overall diagnosis (*e.g.*, increased creatinine levels in renal failure), only the diagnosis should be reported as an AE.

Elective procedures (surgeries or therapies) that were scheduled prior to the start of AE collection are not considered AEs. These elective procedures should not be recorded as AEs, but should be documented in the subject’s source documents as elective (*e.g.*, elective periodontal surgery). However, if a pre-planned procedure is performed early (*e.g.*, as an emergency) because of a worsening of the preexisting condition, the worsening of the condition should be captured as an AE.

11.7. Reporting Serious Adverse Events

Any AE the investigator considers serious according to the previously described criteria must be reported within 24 hours from the time the site personnel first learn about the event. The eCRF system within the clinical database is the preferred method of reporting an SAE.

To report the SAE, the investigator will complete the SAE form in the clinical database and submit to BSWRI Safety (Refer to [Table 5](#)) within 24 hours of awareness. If the clinical database is down for any reason, the manual SAE forms should be used; however, sites are responsible for ensuring the information on the manual SAE forms is entered into the clinical database once available.

Table 5: SAE Reporting Contact Information

BSWRI Safety Hotline North America Safety Hotline: Safety Fax: E-mail:

For questions regarding SAE reporting, contact your study manager, monitor, or BSWRI Safety.

Follow-Up Reports

The investigator must continue to follow the subject until the SAE has subsided or until the condition becomes chronic in nature, stabilizes (in the case of persistent impairment), or the subject dies.

Within 24 hours of receipt of new information, the SAE form should be updated within the clinical database and submitted along with any supporting documentation (*e.g.*, subject discharge summary or autopsy reports) to BSWRI Safety NA (refer to [Table 5](#)). If the clinical database is down for any reason, the manual SAE forms should be used; however, sites are responsible for ensuring the updated information on the manual SAE forms is entered into the clinical database once available.

The Sponsor or designee will notify regulatory agencies of any fatal or life-threatening unexpected events associated with the use of the study drug as soon as possible but no later than 7 calendar days after the initial receipt of the information. Initial notification will be followed by a written report within the timeframe established by the appropriate regulatory agency. For other SAEs that do not meet the fatal or life-threatening unexpected criteria, but are reported to be associated with the use of the study drug, BSWRI or designee will notify the appropriate regulatory agencies in writing within the timeframe established by those regulatory agencies. BSWRI or designee will provide copies of any reports to regulatory agencies regarding serious and unexpected SAEs to the investigators for review and submission to their institutional review board (IRB) or Ethics Committee (EC), as appropriate.

Principal investigators are responsible for informing their IRB/EC of any SAEs at their site. SAE correspondence with regulatory authorities or IRBs/ECs must be submitted to the Sponsor or designee for recording in the study file.

These events will be reviewed on a regular basis in aggregate and will be reported in an expedited manner if a safety signal is detected. Regular safety study updates will be reported to regulatory authorities according to local guidelines.

12. STATISTICS

12.1. Sample Size

A total sample of 360 individuals (180 in each arm) would provide at least 80% power to detect a relative risk reduction of 40% in the rate of positive NP samples when the anticipated rate of positive conversion among those taking hydroxychloroquine is approximately 30%.

The power calculation, which was based on Pearson Chi Square test, assumes the following:

- One-sided Type I error rate of 0.05
- Anticipated positive NP samples rate of 30% in the clinical arm
- A 40% lower risk of a positive NP sample comparing the hydroxychloroquine group vs the controls
- Loss to follow-up rate of 15%

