2. Unwilling to practice acceptable methods of birth control (both males who have partners of childbearing potential and females of childbearing potential) during Screening, while taking study drug, and for at least 30 days after the last dose of study drug is ingested

Note: the following criteria follow standard clinical practice for FDA approved indications of this medication

3. Having a prior history of blood disorders such as aplastic anemia, agranulocytosis, leukopenia, or thrombocytopenia
4. Having a prior history of glucose-6-phosphate dehydrogenase (G-6-PD) deficiency
5. Having dermatitis, psoriasis or porphyria
6. Taking Digoxin, Mefloquine, methotrexate, cyclosporine, praziquantel, antacids and kaolin, cimetidine, ampicillin, Insulin or antidiabetic drugs, arrhythmogenic drugs, antiepileptic drugs, loop, thiazide, and related diuretics, laxatives and enemas, amphotericin B, high dose corticosteroids, and proton pump inhibitors, neostigmine, praziquantel, Pyridostigmine, tamoxifen citrate
7. Allergies: 4-Aminoquinolines
8. Pre-existing retinopathy of the eye
9. Has a chronic liver disease or cirrhosis, including hepatitis B and/or untreated hepatitis
10. Untreated or uncontrolled active bacterial, fungal infection
11. Known or suspected active drug or alcohol abuse, per investigator judgment
12. Women who are pregnant or breastfeeding
13. Known hypersensitivity to any component of the study drug
14. A known history of prolonged QT syndrome or history of additional risk factors for torsades de pointe (e.g., heart failure, requires a lab test , family history of Long QT Syndrome), or the use of concomitant medications that prolong the QT/QTc interval

Investigational product, dosage and mode of administration:

Oral hydroxychloroquine 400 mg twice a day (two 200 mg tabs twice a day) on day 1 followed by two 200 mg tablets once a week for a total of 7 weeks.

Duration of treatment:

Study drug will be administered for 7 weeks.

Criteria for evaluation:

Efficacy: Rate of COVID-19 positive conversion on weekly nasopharyngeal (NP) sampling

Safety: Body temperature measurements, adverse events, and serious adverse events.

Statistical methods:

Sample size: A total sample of 360 individuals (180 in each arm) would provide at least 80% power to detect a relative risk reduction of 40% in the rate of positive NP samples when the anticipated rate of positive conversion among those taking hydroxychloroquine is approximately 30%.

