The power calculation, which was based on Pearson Chi Square test, assumes the following:

- One-sided Type I error rate of 0.05
- Anticipated positive NP samples rate of 30% in the clinical arm
- A 40% lower risk of a positive NP sample comparing the hydroxychloroquine group vs the controls
- Loss to follow-up rate of 15%

Primary analysis of efficacy:

The proportion of individuals who tested positive at least once during the study period will be compared between the clinical and the control arms. In addition, the potential effect of hydroxychloroquine on COVID-19 free survival time will also be explored by utilizing appropriate statistical methods. An intent-to-treat approach will be used throughout the analysis with the control group as the referent. A p-value < 0.05 will be considered statistically significant and a risk reduction of 5% will be considered as of smallest clinical importance.

Study Rationale

It is clear that close interaction of health care workers with patients put them at higher risk of getting exposed to infectious diseases. Failing to provide a safe environment for health care workers could cripple the medical system especially during an Epidemic outbreak like COVID-19. It is imperative to make sure that doctors and nurses do not get sick in high numbers; not only because that will contribute to spreading the virus among vulnerable patients but also due to their subsequent role in reducing the number of responding personnel. As a result, it is of utmost importance to provide effective prophylaxis to healthcare workers who are exposed to COVID-19.

Schema for Study of Prophylactic Therapies for COVID-19 Exposure

The trial design is initially for a 7 week treatment period which can be divided into 7 bins of time to allow a flexible design. Given the fluid nature of information flow in this pandemic that for example, new information comes forward clearly showing that 6 days is a sufficient period of time for proven prophylaxis, this trial design can be altered. Conversely if each subsequent qualifying exposure calls for another 6-day bin of time, the protocol can flex to the maximum 7 week period as stated for resource planning.

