7.3. Treatment Assignment

Qualified individuals may choose which group they want to be in. Subjects in the treatment group will receive hydroxychloroquine for 7 weeks. Those who decide to opt out of receiving treatments will compose the control group.

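### The listed sample-size inputs give about 85–88 enrolled per arm, not the stated 180; the 30% rate was probably meant for the control arm

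*Protocol*

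**What the plan says.** The same sample-size paragraph stands in the protocol synopsis, Protocol 12.1 and SAP 2.1. It says "A total sample of 360 individuals (180 in each arm) would provide at least 80% power to detect a relative risk reduction of 40" per cent, based on a Pearson chi-square test. The listed assumptions are:

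- for the event rate on treatment: "Anticipated positive NP samples rate of 30% in the clinical arm"
- for the test level: "One-sided Type I error rate of 0.05"
- for the size of the effect: "A 40% lower risk of a positive NP sample comparing the hydroxychloroquine group vs the controls"
- for attrition: 15% of subjects lost

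The lead sentence also ties the rate to the treated subjects: "when the anticipated rate of positive conversion among those taking hydroxychloroquine is approximately 30" per cent. The synopsis confirms that subjects in the clinical arm are those who receive hydroxychloroquine. No control rate is given anywhere.

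Three other statements bear on the power. The synopsis sets the decision rule, "A p-value < 0.05 will be considered statistically significant", without saying whether the test is one- or two-sided; Protocol 12.2 and SAP section 6 name the chi-square and Fisher tests, also without sidedness. The synopsis plans equal groups ("360 individuals will be enrolled into the study with half enrolling in the active treatment study"). Protocol 7.3 leaves the group to the subject ("Qualified individuals may choose which group they want to be in"), and Appendix I does not fix the size of the registry.

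**The concern.** The assumptions are presented as the basis for 360, so a reader should be able to get from them to 180 per arm. With 30% on hydroxychloroquine and a relative risk of 0.60, the contrast is 30% vs 50%. That is a 20-point difference, which needs far fewer than 180 per arm for 80% power. Either an input is misreported or the number came from a different calculation.

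The two explanations have very different consequences. If the written rates are right, the trial has about 97.5% power and the reason for enrolling 360 is missing. If 30% was the control rate, the trial has no margin over 80% even one-sided, and falls about 10 points short if the primary test is two-sided. A null result would be read quite differently in the two cases.

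**Working it through.** **Inputs** (Protocol 12.1, SAP 2.1): relative risk 0.60; one-sided 0.05 (z = 1.645); 80% power (z = 0.842); 15% loss; 180 enrolled per arm.

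**Formula**, evaluable n per arm, pooled-variance chi-square, with p̄ the mean of p₁ and p₂:

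n = [z_α √(2p̄(1−p̄)) + z_β √(p₁(1−p₁) + p₂(1−p₂))]² / (p₁ − p₂)²

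**1. The plan's figure from its written inputs.** Control rate = 0.30/0.60 = 0.50 and p̄ = 0.40.

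n = [1.645 × √0.48 + 0.842 × √0.46]² / 0.20² = (1.1396 + 0.5708)² / 0.04 = 73.14, so 74 evaluable per arm.

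The plan does not say how the 15% was applied. Dividing by 0.85 gives 74/0.85 = 87.1, so 88. Multiplying by 1.15 gives 73.14 × 1.15 = 84.1, so 85 (86 if n is first rounded to 74). The result is about 85–88 enrolled per arm, and the stated 180 is not reproduced.

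Other methods do not rescue it. At 80% power with the written rates, the enrolled number per arm (dividing by 0.85) is:

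| Method | Enrolled per arm |
|---|---|
| Unpooled variance, one-sided | 85 |
| Arcsine, one-sided | 88 |
| Continuity-corrected, one-sided | 98 |
| Exact Fisher, one-sided | about 98–100 |
| Chi-square, two-sided | 110 |
| Continuity-corrected, two-sided | 122 |

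Two other readings of the effect, at one-sided 80% power, also miss: an additive one (42% vs 30%) needs 232, and an odds ratio of 0.6 needs 245.

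**2. Moving only the 30% to the control arm.** Hydroxychloroquine rate = 0.30 × 0.60 = 0.18 and p̄ = 0.24.

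n = [1.645 × √0.3648 + 0.842 × √0.3576]² / 0.12² = (0.9935 + 0.5033)² / 0.0144 = 155.57, so 156 evaluable per arm.

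Enrolled: 156/0.85 = 183.5, so 184; or 155.57 × 1.15 = 178.9, so 179 (180 if n is first rounded to 156). This closely reproduces 180 with the stated test, alpha, power and loss unchanged.

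**3. A competing reconstruction.** 30% vs 50%, two-sided 0.05, 95% power: n = 152.95, and 152.95/0.85 = 179.9. This also gives 180, but it contradicts two stated inputs (one-sided and 80%).

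**4. Power of 180 enrolled per arm.** Evaluable: 180 × 0.85 = 153, or 180/1.15 = 156.5.

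Power = Φ{ [|p₁ − p₂| − z_α √(2p̄(1−p̄)/n)] / √([p₁(1−p₁) + p₂(1−p₂)]/n) }

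For 18% vs 30% at n = 153, one-sided: (0.12 − 1.645 × 0.04883)/0.04835 = 0.821, so 79.4%.

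| Rates (hydroxychloroquine vs control) | Test | n = 153 | n = 156.5 |
|---|---|---|---|
| 30% vs 50% | one-sided | 97.5% | 97.8% |
| 30% vs 50% | two-sided | 95.0% | 95.4% |
| 18% vs 30% | one-sided | 79.4% | 80.2% |
| 18% vs 30% | two-sided | 69.2% | 70.2% |

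Exact enumeration of the Pearson test at 153 per arm agrees: 97.4% and 95.2% for 30% vs 50%, and 79.8% and 69.5% for 18% vs 30% (one- and two-sided).

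**5. Unequal arms.** The documents plan equal arms, so a 2:1 split is my assumption, used only to show sensitivity to self-selection. With 306 evaluable split 204/102 in either direction, 18% vs 30% gives 74–76% one-sided and 62–66% two-sided. 30% vs 50% gives 96% and 92–93%.

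**The case against.** The strongest reply is that nothing stated is false. At least 80% power is a lower bound, and 97.5% satisfies it. That is correct and limits the finding: the provable fault is that inputs offered as the basis for 180 do not produce it, and that the 50% control rate they imply is not stated.

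A second reply is that the misplaced rate is conjecture. Two differently worded statements tie 30% to hydroxychloroquine, both recur in all three places, and none gives 30% as a control rate. The reconstruction is also imperfect: with the usual division by 0.85 it needs 184 per arm, and 153 evaluable gives 79.4%, just under 80%. This stands as a reason to ask the sponsor. The repetition is weak evidence, though, because the three paragraphs are nearly identical, and the rival match requires two stated inputs to be wrong where this one requires one.

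Third, the two-sided shortfall depends on two unconfirmed conditions, and the only sidedness written is one-sided. That is also fair. On the written rates two-sided power is still 95.0%, so the missing sidedness matters only if 30% is the control rate.

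Finally, the enrolled range depends on method and rounding (83 to about 100 across the one-sided versions tried). None comes near 180.

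**Conclusion.** The concern holds. As written, the inputs require 74 evaluable, or about 85–88 enrolled, per arm, about half of the stated 180. That part is definite and rests only on the stated assumptions and the standard chi-square formula.

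That 30% belongs to the control arm is a well-supported inference, not a proven fact. If it is right, power for 360 enrolled is about 79–80% one-sided and about 69–70% two-sided, instead of 97.5% and 95.0%. All these figures assume equal arms, 15% loss in each arm and the stated 40% relative reduction. The defect should be fixed: the power claim is not false, but its basis cannot be reproduced, and the reader cannot tell which of two very different designs was intended.

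**What to change.** Make the same change in the synopsis, Protocol 12.1 and SAP 2.1:

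1. State the expected positive rate in each arm. If 30% was the control rate, move it there and give 18% for hydroxychloroquine.
2. State how the 15% loss was applied (division by 0.85 or multiplication by 1.15).
3. Add the design's sidedness to the p < 0.05 rule, which now stands only in the synopsis, and carry it into Protocol 12.2 and SAP section 6.
4. Restate the chi-square power for 360 enrolled to match: about 97.5% one-sided or 95% two-sided for 30% vs 50%; about 79–80% one-sided or 69–70% two-sided for 18% vs 30%.
5. Say that these figures assume equal arms, since subjects choose their group.

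Correcting the text needs no added enrolment. The cost is that the stated power may become less favourable. If the sponsor confirms 18% vs 30% with a two-sided test, the 80% claim has to come down to about 69–70%. Keeping it would take 198 evaluable per arm, which is 233 enrolled (198/0.85 = 232.9) or 228 (198 × 1.15 = 227.7).
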